# 9.7 Health Economics OR Medical Resource Utilization and Health Economics

Health Economics/Medical Resource Utilization and Health Economics parameters will not be evaluated in this study.

#### 10 STATISTICAL CONSIDERATIONS

#### 10.1 Sample Size Determination

In determining the sample size for the IPF cohort, both statistical considerations and clinical feasibility criteria were utilized. Among the considerations were:

Protocol Amendment No.: 05

- Sizing of published early phase trials in IPF.
- Precision to estimate the difference of the 30 mg BID and 60 mg BID doses to placebo on the primary efficacy measure of ppFVC.
- The assumption that a 2.5% difference in ppFVC (favoring 30 mg BID or 60 mg BID vs placebo) would be meaningful and that the standard deviation of this difference would 6.5%.
- The assumption that 80% of participants randomized will complete the 26-week treatment period.
- PK and tolerability data will be key factors in the selection of a dose for further evaluation. Given the limitations on participant recruitment and resulting sample size, it is not anticipated that the 30 mg BID and 60 mg BID cohorts will be differentiated relative to FVC.

95% two-sided confidence intervals were computed for a range of sample sizes. The confidence level was based on an overall Type 1 error of 0.10, with 0.05 allocated to each dose comparison (30 mg BID and 60 mg BID) relative to placebo. The resulting confidence intervals are described in Table 10.

Table 10: 95% CI of the Absolute Difference in ppFVC (%) Between BMS-986278 (30 mg BID or 60 mg BID) Compared to Placebo Based on an Observed Difference of 2.5%

Sample Size per Arm	Lower Bound 95% CI	Upper Bound 95% CI
60	0.17	4.83
80	0.49	4.51
100	0.70	4.30

CI = confidence interval

Based on these considerations, a sample size of 80 participants per arm was selected. Note that for all sample sizes, the lower bound of the 95% confidence interval excludes zero, consistent with a nominal p-value < 0.05. For the purposes of this study, if either dose comparison achieves a p-value of 0.05 or less, it will be described as "statistically significant."

With regards to the PF-ILD cohort, statistical considerations were not utilized. A total of 120 participants will be enrolled. A target of enrolling 75 out of 120 (62.5%) with UIP pattern is expected and randomization will be stratified by UIP pattern (present versus absent) and by category of background therapy (ILD-targeted immunosuppression [ie, azathioprine, mycophenolate mofetil, mycophenolic acid, and/or tacrolimus] alone versus anti-fibrotics [nintedanib, pirfenidone] with or without ILD-targeted immunosuppression versus no ILD-targeted immunosuppression or anti-fibrotics). These participants will be analyzed separately and considered as supportive to the findings within the IPF cohort.

Protocol Amendment No.: 05

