# 5.1.3 Main Study Posttreatment Follow-up Period

Participants in the main study that do not enter the OTE will undergo a posttreatment follow-up visit 28 days (± 7 days) after the Week 26 visit. During the follow-up period, participants will not receive either active treatment or placebo.

Participants in the main study that discontinue study treatment with BMS-986278 or matching placebo before Week 26 will complete the remaining study visits according to the Schedule of Activities (Table 1), including the posttreatment follow-up visit.

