# 5.2 Number of Participants

This study will randomize approximately 360 participants in total.

Approximately 240 participants with IPF will be randomized to receive 30 mg BMS-986278 BID, 60 mg BMS-986278 BID, or placebo BID at a ratio of 1:1:1 for 26 weeks in the main study.

In addition, a secondary cohort of approximately 120 PF-ILD participants will be randomized to receive 30 mg or 60 mg BMS-986278 BID or placebo BID at a ratio of 1:1:1 for 26 weeks in the main study.

Following the 26-week main study, participants from both IPF and PF-ILD cohorts will have the opportunity to participate in an additional 26-week OTE. All participants in the OTE will receive an active dose of BMS-986278 (30 mg BID, 60 mg BID, or 10 mg BID).

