## 8.1.1 Posttreatment Follow-up

Posttreatment follow-up is of critical importance and is essential to preserving participant safety and the integrity of the study. Participants who discontinue study treatment must continue to be followed according to the protocol.

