## 10.2 Populations for Analyses

For purposes of analysis, the following populations are defined:

Population	Description
Enrolled	All participants who sign informed consent.
Full Analysis Set (FAS)	All participants who are randomized and receive at least 1 dose of study treatment. Participants will be analyzed according to the treatment group assigned at randomization. The FAS will be the primary efficacy analysis population.
Pharmacokinetic	All randomized participants who receive at least 1 administration of BMS-986278 and have any quantifiable concentration data.
Safety	All participants who are randomized and receive at least 1 dose of study treatment. Participants will be analyzed according to the treatment group assigned; participants who receive incorrect study treatment will be analyzed according to the actual treatment received.

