## 10.4.5 Interim Analyses

An interim analysis is planned for the IPF cohort when approximately 50% of participants (N = 40/arm) complete Week 26. This analysis will be performed and results reviewed by the independent DMC. No formal test of statistical significance is planned given the limited sample size at Week 26. Results will be descriptive and based on estimation of effect size and associated confidence intervals. Thus, no adjustments to overall type I error will be made. Further details on statistical considerations, review of data, and unblinding will be included in the DMC Charter and SAP.

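### Should Table 10's precision figures have been reduced for the assumed 80% treatment completion?

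*Combined protocol and SAP*

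**What the plan says.** Section 10.1 of the protocol gives no power calculation. It bases the IPF cohort on precision and feasibility, and lists several considerations. One is a 2.5-point difference in ppFVC, with the statement that "the standard deviation of this difference would 6.5" percent. Another is "The assumption that 80% of participants randomized will complete the 26-week treatment period".

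Table 10 then gives 95% confidence intervals for an observed difference of 2.5 at 60, 80 and 100 per arm. The column heading says only that these are sizes per arm. The text selects 80 and adds that "for all sample sizes, the lower bound of the 95% confidence interval excludes zero, consistent with a nominal p-value < 0.05".

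The selected 80 is a randomised count. Section 5.2 says "Approximately 240 participants with IPF will be randomized to receive 30 mg BMS-986278 BID, 60 mg BMS-986278 BID, or placebo BID", equally allocated, and Section 10.4.5 says "An interim analysis is planned for the IPF cohort when approximately 50% of participants (N = 40/arm) complete Week 26".

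On follow-up, Section 5.1.3 says that main-study participants who stop treatment "before Week 26 will complete the remaining study visits according to the Schedule of Activities (Table 1"), and Section 8.1.1 says "Participants who discontinue study treatment must continue to be followed according to the protocol". Section 5.3 counts a participant as completing the main study after 26 weeks of evaluation; it does not require 26 weeks of treatment. Section 10.2 defines the FAS as everyone randomised and dosed, and says "The FAS will be the primary efficacy analysis population". Section 10.4.1.1 fits a random-coefficient model to ppFVC at every visit, without imputation.

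**The concern.** An assumption listed for sizing would normally appear in the sizing figures. Here it does not, and the section neither applies it nor sets it aside. Table 10 holds the only precision figures given for the chosen size, so a reader may reasonably ask whether they are too favourable.

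The sentence about all three sizes is also written without conditions. If the missing 20% supplied nothing, it would be untrue for one of the three rows. At the chosen size the half-width would grow by about 12%. If 80 per arm had been adequate only because attrition was overlooked, the cohort would be too small for its stated purpose.

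**Working it through.** **Inputs.** All are from Section 10.1: observed difference 2.5, SD 6.5, two-sided 95% level, sizes 60, 80 and 100 per arm, 80% completing treatment.

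**Reproducing Table 10.** Half-width = 1.96 × 6.5 × √(2/n), at the full n:

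| n per arm | SE | Computed interval | Printed |
|---|---|---|---|
| 60 | 1.187 | 0.174 to 4.826 | 0.17 to 4.83 |
| 80 | 1.028 | 0.486 to 4.514 | 0.49 to 4.51 |
| 100 | 0.919 | 0.698 to 4.302 | 0.70 to 4.30 |

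All six bounds match. Taking 6.5 literally as the SD of the difference (SE = 6.5/√n) gives lower bounds of 0.86, 1.08 and 1.23, which do not match. The table therefore treats 6.5 as the per-participant SD in each arm, and the loose wording resolves itself.

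**Are the sizes completers?** No. Having 80 completers at 80% completion would need 80/0.8 = 100 randomised per arm, or 300 in total. The protocol randomises 3 × 80 = 240.

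**If only 80% contributed data**, same formula:

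| Randomised | Contributing | Interval | p |
|---|---|---|---|
| 60 | 48 | −0.10 to 5.10 | 0.060 |
| 80 | 64 | 0.25 to 4.75 | 0.030 |
| 100 | 80 | 0.49 to 4.51 | 0.015 |

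At 80 per arm the half-width goes from 2.01 to 2.25, a ratio of √(80/64) = 1.12.

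**Break-even.** The lower bound reaches zero at n = 2 × (1.96 × 6.5/2.5)² = 51.9, so 52 contributing per arm suffice. That is 87% of 60 but only 65% of 80.

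**What the planned model would do.** The two-group formula discards anyone without a final value. The random-coefficient model keeps every visit made. To see the difference I used assumptions that are not in the documents:

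- 6.5 is the SD of change from baseline to Week 26.
- The residual SD r lies between 1.5 and 3.5.
- The intercept SD is 15.
- Missingness is ignorable.

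Visits are at Weeks 0, 4, 8, 12, 16, 20 and 26. With t in units of 26 weeks, Σ(t − t̄)² = 0.739. The variance of the true slopes is 6.5² − 2r², and a complete participant's fitted slope has variance 6.5² − 2r² + r²/0.739. Its SD is therefore √(42.25 − 4.5 + 3.05) = 6.39 at r = 1.5 and √(42.25 − 24.5 + 16.58) = 5.86 at r = 3.5.

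Lower 95% bound across that range of r:

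| Data pattern | 60 per arm | 80 per arm |
|---|---|---|
| Complete | 0.21 to 0.40 | 0.52 to 0.68 |
| 20% leave, last visit spread evenly from Day 1 to Week 20 | 0.10 to 0.23 | 0.42 to 0.54 |
| 20% leave, all last seen at Week 12 | 0.15 to 0.24 | 0.46 to 0.54 |
| 20% leave, all last seen at Week 4 | 0.00 to 0.17 | 0.34 to 0.48 |
| The 20% discarded entirely | −0.06 to 0.16 | 0.29 to 0.47 |

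A bound below zero at 60 per arm appears only in the last row, which throws away visits the plan keeps. At 80 per arm no pattern brings the bound near zero.

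**The case for a change.** The strongest case for a change is that the section lists the 80% as a sizing consideration and never uses it. If the mixed model makes treatment completion irrelevant to precision, the protocol could say so. As printed, the sentence about all sizes rests on an unstated condition of complete data, and under the section's own method it fails at 60 per arm once fewer than 52 contribute. One label and one qualifying sentence would cost almost nothing.

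Much of this stands. The table does assume complete data, the heading does not say so, and the 80% is left hanging. Some participants will also be lost to all visits, through death or withdrawal of consent, so precision will probably fall somewhat short of complete data.

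What does not stand is the step from there to a defect. The sentence describes the three printed rows and is true of each. Section 10.1 never says that Table 10 incorporates the 80%. No power is claimed, so no target is missed. A second column at 48, 64 and 80 would describe a completers analysis that the plan does not contain, and could lead readers to expect one.

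A separate point is that data collected after stopping treatment may dilute the treatment difference. Table 10 is conditional on an observed 2.5, so that affects the size of the effect and not the precision at issue here.

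**Conclusion.** The observation is accurate, but no change is needed. Table 10 is a two-group approximation at the full randomised size, and its six bounds are correct on that footing. The assumption it leaves out concerns completing treatment, while the protocol keeps collecting and analysing data after treatment stops. An analyst reading Section 10.1 with Sections 5.1.3, 8.1.1 and 10.4.1.1 can see what the table represents.

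The decision that rests on the table is robust. At 80 randomised per arm the lower bound is 0.49 with complete data and 0.25 in the pessimistic case where one-fifth contribute nothing; zero is excluded until fewer than about 65% contribute. The only sensitive statement concerns 60 per arm, which was not chosen. The total of 240, the primary model, the 0.05 rule for each dose and the conclusion at 80 per arm all stand.

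The two-group results rest only on the figures in Section 10.1. The slope-model results rest on the assumed residual and intercept SDs and on ignorable missingness, and serve as illustration. A sponsor revising the section for other reasons could label the column as randomised per arm with complete data. That would be a courtesy to readers and would change no number or decision.

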## 10.2 Populations for Analyses

For purposes of analysis, the following populations are defined:

Population	Description
Enrolled	All participants who sign informed consent.
Full Analysis Set (FAS)	All participants who are randomized and receive at least 1 dose of study treatment. Participants will be analyzed according to the treatment group assigned at randomization. The FAS will be the primary efficacy analysis population.
Pharmacokinetic	All randomized participants who receive at least 1 administration of BMS-986278 and have any quantifiable concentration data.
Safety	All participants who are randomized and receive at least 1 dose of study treatment. Participants will be analyzed according to the treatment group assigned; participants who receive incorrect study treatment will be analyzed according to the actual treatment received.

## 10.3 Endpoints

## 10.3.1 Primary Endpoints

The primary endpoint is the rate of change in ppFVC (%) in IPF participants, estimated from measurements taken over 26 weeks of treatment. The decrease in ppFVC is assumed to be linear within each participant over the 26 weeks.

## 10.3.2 Secondary Endpoints

Secondary endpoints are as follows:

#### **Safety Assessments:**

- AEs
- SAEs
- AEs leading to early discontinuation of study treatment
- Treatment-emergent deaths
- Clinical laboratory findings and ECGs
- Vital signs
- Physical exam findings

### **Efficacy Endpoints:**

- PF-ILD cohort only:
  - Rate of change in ppFVC (%) in PF-ILD participants will be estimated from measurements taken over 26 weeks of treatment. The decrease in ppFVC is assumed to be linear within each participant over the 26 weeks.

Protocol Amendment No.: 05

#### IPF and PF-ILD cohorts:

- Proportion of participants with a at least 10% absolute decline from baseline in ppFVC (%) at Weeks 4, 8, 12, 16, 20, and 26
- Proportion of participants with > 0% change in ppFVC at Weeks 4, 8, 12, 16, 20, and 26
- Time to first acute exacerbation
- Time to first occurrence ≥ 10% absolute decline in ppFVC (%)
- Absolute change in ppFVC (%) from baseline to Week 26
- Absolute change in FVC (mL) from baseline to Week 26
- Absolute change in DLCO SB (mL/min/mmHg) (corrected for hemoglobin) from baseline to Week 26
- Absolute change in ppDLCO SB (%) (corrected for hemoglobin) from baseline to Week 26
- Change in walking endurance/distance from baseline at Week 26 as measured using the 6MWT
- Proportion of participants with acute exacerbations (evidence of which will be captured in the eCRF) of lung fibrosis defined as an acute, clinically significant, respiratory deterioration characterized by evidence of new widespread alveolar abnormality, as follows:
  - 1. Acute worsening or development of dyspnea (< 1 month duration)
  - 2. Imaging with new bilateral ground-glass opacity and/or consolidation superimposed on a background pattern consistent with fibrotic lung disease.
  - 3. Respiratory deterioration not fully explained by cardiac failure of fluid overload

#### BMS-986278 PK Parameters:

- Cmax
- Tmax
- AUC(0-8)
- Ctrough

#### 10.3.3 Exploratory Endpoints

Exploratory endpoints in the main study and/or OTE include but are not limited to the following: HRCT:

• Change in QLF using the Quantitative HRCT Fibrosis Score from baseline to Week 26

#### COAs:

- Change in HRQoL from baseline at each assessment timepoint during treatment as measured by the L-PF
- Change in HRQoL from baseline at each assessment timepoint during treatment as measured by the SGRQ

Protocol Amendment No.: 05

 Change in dyspnea from baseline at each assessment timepoint during treatment as measured by the UCSD SOBQ

- Change in cough severity from baseline at each assessment timepoint during treatment as measured using a VAS
- Change in walking endurance/distance from baseline at each assessment timepoint during treatment as measured using the 6MWT

#### PK:

- Cmax, Tmax, and AUC(0-8) on Day 1 and Week 4 and Ctrough on Week 4 and Week 12 of intensive PK substudy
- Plasma concentrations of nintedanib and pirfenidone in participants who receive nintedanib or pirfenidone alone and co-administered with BMS-986278
- Plasma concentrations of the BMT-323719 metabolite (including but not limited to AUC(0-8), Ctrough, Cmax, and Tmax of intensive PK study)

#### Disease Outcomes:

- Composite endpoint of time to first all-cause hospitalization or overall survival
- Pulmonary fibrosis progression-free survival (pulmonary fibrosis progression is defined as any of the following: ≥ 10% decline in ppFVC relative to baseline, ≥ 50 m decline in 6MWT relative to baseline, lung transplantation, or death)

#### Clinical Assessments of Disease:

- Proportion of participants with > 5% decline in FVC (mL) relative to baseline
- Proportion of participants with > 10% decline in FVC (mL) relative to baseline
- Proportion of participants with > 5% absolute decline in ppFVC (%)
- Proportion of participants with > 5% decline in ppFVC (%) relative to baseline
- Proportion of participants with > 10% decline in ppFVC (%) relative to baseline
- Time to first > 5% absolute decline in ppFVC (%)
- Time to first > 5% decline in ppFVC (%) relative to baseline
- Time to first > 10% decline in ppFVC (%) relative to baseline
- Time to first > 5% decline in FVC (mL) relative to baseline
- Time to first > 10% decline in FVC (mL) relative to baseline

#### Biomarkers:

- Change from baseline of blood-based biomarkers (including gene expression profiles) of lung fibrosis and inflammation
- Presence or absence of single nucleotide variants in genes associated with lung fibrosis

Protocol Amendment No.: 05

• Presence or absence of SNP variants in genes encoding organic anion transporting polypeptides, CYP 2C8, and breast cancer resistance protein

• Exploratory measurements of SARS-CoV-2 serology (anti-SARS-CoV-2 total or IgG) from serum samples collected at baseline, main study completion, and end of the OTE

#### 10.4 Statistical Analyses

The Statistical Analysis Plan (SAP) will be developed and finalized before first unblinding event of the study (see Section 10.4.5), and will provide detailed specifications of the analysis of all efficacy endpoints and safety data. This section provides a summary of planned statistical analyses.

Categorical data will be summarized using counts and percentages. Continuous data will be summarized using n, mean, standard deviation, median, minimum, and maximum unless otherwise specified.

## 10.4.1 Efficacy Analyses

## 10.4.1.1 Primary Efficacy Endpoint

The primary endpoint is the rate of change in ppFVC in IPF participants (estimated from measurements taken over 26 weeks of treatment). The decrease in ppFVC is assumed to be linear within each participant over the 26 weeks.

The primary analysis will compare the rate of change in ppFVC from baseline to Week 26 using a random coefficient linear mixed model using the Full Analysis Set (FAS). The model will include ppFVC at each visit as dependent variable, random coefficients for intercept and slope and fixed effect terms for treatment, time since randomization, treatment × time interaction, and baseline stratification factors. No imputation of missing values will be performed for the primary analysis. Sensitivity analysis may be performed to assess the impact of missing values as well as impact of dose reduction on the primary analysis. There will be no adjustment for multiple comparisons.

Subgroup analyses will be performed for concomitant use of pirfenidone or nintedanib therapy (vs neither pirfenidone nor nintedanib) for IPF and for other demographic and baseline characteristics.

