## 10.4.1.2 Secondary Efficacy Endpoints

All secondary analyses will be based on the FAS population. As appropriate, continuous secondary endpoints will be analyzed using mixed model repeated measures (MMRM) with a random effect for participant and fixed effects for treatment, visit, treatment-by-visit interaction, and baseline stratification factors. The baseline value of the endpoint being tested will be added into the model as a covariate. In addition, as appropriate analysis of covariance models will be used to analyze continuous secondary endpoints with treatment and factors used for randomization as fixed effects. The baseline value will be added into the model as a covariate.

Cochran-Mantel-Haenszel tests will be used to compare dichotomous endpoints between either BMS-986278 dose group vs placebo.

The Kaplan-Meier product limit method will be used to estimate the survival curves for time-to-event endpoints. Treatment comparisons between each BMS-986278 dose group and placebo will be performed using the log-rank test stratified by baseline stratification factors.

The PF-ILD cohort will be analyzed separately from the primary study cohort of IPF. The PF-ILD statistical analysis methods will be similar to IPF cohort. The details will be described in the SAP.

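### The primary slope model, though valid, fits a separate intercept per arm with no baseline × time term and does not say whether Day 1 ppFVC is a response; a common intercept is a free gain of 0% to about 11% in variance

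*Combined protocol and SAP*

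**What the plan says.** Section 10.4.1.1 defines the primary contrast: "The primary analysis will compare the rate of change in ppFVC from baseline to Week 26 using a random coefficient linear mixed model". The terms are "random coefficients for intercept and slope and fixed effect terms for treatment, time since randomization, treatment × time interaction, and baseline stratification factors". No baseline ppFVC term or baseline × time term is listed. The response is ppFVC at each visit, without a statement on whether Day 1 counts as one of those visits.

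Section 10.4.1.2 treats the continuous secondary endpoints differently. For the MMRM, "The baseline value of the endpoint being tested will be added into the model as a covariate"; for the ANCOVA, "The baseline value will be added into the model as a covariate". For the second cohort, "The PF-ILD statistical analysis methods will be similar to IPF cohort", so the PF-ILD rate of change in ppFVC (a secondary endpoint in Section 10.3.2) presumably uses the same slope model as the primary.

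Section 10.4 presents all this as a summary and says that the SAP "will provide detailed specifications of the analysis of all efficacy endpoints and safety data". The combined document holds no further SAP text on this model. Section 9.1.1 places spirometry before the morning dose, and Table 1 schedules it on Day 1 and at Weeks 4, 8, 12, 16, 20 and 26.

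**The concern.** The treatment main effect lets each arm have its own mean at time 0. Treatment has not started then and allocation is random, so the true difference is zero. Estimating it can cost precision on the treatment × time contrast, because fitted intercepts and fitted slopes are correlated. There are two sources of that correlation: a real association between starting level and rate of decline, and measurement error in the early values, which tilts the fitted line. Through the same two routes, part of a chance baseline imbalance can reach the slope contrast.

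The primary analysis is the one behind the per-dose significance rule in Section 10.1 ("overall Type 1 error of 0.10, with 0.05 allocated to each dose comparison"). Avoidable imprecision therefore matters more here than elsewhere.

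**Working it through.** **The plan's own figure.** Section 10.1 gives a difference of 2.5, SD 6.5 and 80 per arm. The interval is 2.5 ± 1.96 × 6.5 × √(2/n):
- n = 60: 2.5 ± 2.33, or 0.17 to 4.83
- n = 80: 2.5 ± 2.01, or 0.49 to 4.51
- n = 100: 2.5 ± 1.80, or 0.70 to 4.30

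Table 10 reproduces exactly. At n = 80 the SE is 6.5 × √(2/80) = 1.028. The protocol states no power; Φ(2.5/1.028 − 1.96) is 68%.

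**Set-up.** Time is in units of 26 weeks, with visits at Weeks 0, 4, 8, 12, 16, 20 and 26. Mean time is 0.4725 and the sum of squares about it is Sxx = 0.7388. Write s0 for the between-participant SD at baseline, s1 for the SD of true slopes, se for the residual SD and ρ for the intercept-slope correlation. None of these is in the documents. Assumed ranges: s0 12 to 20, se 2 to 4, ρ −0.3 to +0.3. For each se, s1 is set so that the SD of a participant's fitted slope equals the protocol's 6.5.

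For one participant's fitted line with complete data:
- slope variance V22 = s1² + 1.354 se² = 42.25
- intercept variance V11 = s0² + 0.445 se²
- covariance C = ρ s0 s1 − 0.640 se²

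For two arms of 80:
- separate intercepts: variance = (2/80) V22, so SE = 1.028 for every parameter choice
- common intercept: variance = (2/80)(V22 − C²/V11), a saving of C²/(V11 V22), which is never negative
- expected shift in the separate-intercept contrast for a one-SE imbalance in Day 1 mean: C/√(s0² + se²) × √(2/80)

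**Example: s0 = 15, se = 3, ρ = −0.3.** s1² = 42.25 − 12.18 = 30.07, so s1 = 5.48. V11 = 225 + 4.0 = 229.0. C = −24.67 − 5.76 = −30.43. Saving = 30.43²/(229.0 × 42.25) = 9.6%, so the SE is 0.977. Shift = −30.43/15.30 × 0.158 = −0.31.

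| s0 | se | ρ | Variance saving | SE, common intercept | Power at 2.5 | Shift per one-SE imbalance |
|---|---|---|---|---|---|---|
| 15 | 3 | −0.3 | 9.6% | 0.977 | 72% | −0.31 |
| 15 | 3 | 0 | 0.3% | 1.026 | 68% | −0.06 |
| 15 | 3 | +0.3 | 3.7% | 1.009 | 70% | +0.20 |
| 12 | 4 | −0.3 | 11.1% | 0.969 | 73% | −0.33 |
| 12 | 4 | 0 | 1.6% | 1.019 | 69% | −0.13 |
| 12 | 4 | +0.3 | 0.6% | 1.025 | 68% | +0.08 |
| 20 | 2 | 0 | 0.04% | 1.028 | 68% | −0.02 |

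The 11.1% row is the largest saving in the assumed range, worth about 10 participants per arm (80/0.889 = 90). With 80% completion and losses spread evenly over visits, the separate-intercept SE is 1.08 to 1.11. The saving is then at most 1.7% at ρ = 0 and at most 10.3% at ρ = −0.3.

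**Two checks by simulation (s0 = 15, se = 3).** Adding 5 points to every ppFVC value in one arm left the separate-intercept slope contrast unchanged (2.452 before and after), because the arm intercept absorbs it. Adding baseline ppFVC as a main effect only also left the contrast unchanged.

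**If Day 1 is not a response.** With only the six post-baseline visits, Sxx falls to 0.478 and the fitted-slope variance becomes s1² + 2.091 se². At se = 2.5 this is 33.79 + 13.07 = 46.86, so SE = 1.08. At se = 3.5 it is 25.67 + 25.61 = 51.28, so SE = 1.13. Power at 2.5 is then 64% to 60%. For most of the assumed range this ambiguity matters more than the choice of intercept.

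**The case against.** The strongest reply is that nothing here is an error. Randomisation makes the listed model unbiased, and its confidence interval already allows for chance imbalance. That stands.

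A reader might infer that a chance difference in baseline ppFVC passes whole into the treatment × time contrast. It does not: an imbalance in level goes into the arm intercepts. Only the part acting through intercept-slope correlation or baseline measurement error remains.

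A reader might also set Section 10.4.1.2 against 10.4.1.1 and conclude that every continuous secondary analysis adjusts for baseline while the primary never does. The documents support neither half. The PF-ILD slope is a continuous secondary endpoint and presumably shares the unadjusted model, and Section 10.4 leaves detail to the SAP. Nor is the contrast an inconsistency. MMRM and ANCOVA compare means at a visit, where a baseline main effect removes variance directly; in a slope model the same term does nothing for the contrast.

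The size is also uncertain. The 72% to 73% power figures come from ρ = −0.3, the favourable end of an assumed range, and the documents support neither that sign nor that size. A baseline-adjusted view of ppFVC already exists through the secondary endpoint of absolute change to Week 26.

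Finally, the common intercept relies on the linear decline that Section 10.3.1 assumes. An early step in one arm would affect the two models differently. That is a reason to keep both, not to leave the choice open.

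**Conclusion.** The point holds as an efficiency and specification point, not as a flaw in validity. The gain is 0% to about 11% of the variance of the slope contrast, under 2% if baseline level and slope are uncorrelated. A one-SE baseline imbalance moves the unadjusted contrast by at most about 0.33 points, against a target difference of 2.5. Both ranges rest on the assumed SDs and correlation, on the protocol's 6.5 read as the SD of a participant's 26-week slope, and on linearity. It would be wrong to report the primary analysis as biased, or to promise the upper end of the gain. The change is still worth making: it uses data already scheduled, cannot raise the model-based variance, and settles whether Day 1 is a response.

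**What to change.** Before the first unblinding, state in Section 10.4.1.1 and the SAP that:
- Day 1 ppFVC is a response at time 0;
- the model has one common intercept across arms (no treatment main effect), arm-specific slopes, the stratification factors, and an unstructured covariance for the random intercept and slope;
- the separate-intercept model is run as a sensitivity analysis;
- the PF-ILD slope is analysed in the same way.

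This form keeps all participants in the Full Analysis Set who have any ppFVC value. If a covariate form is preferred, with post-baseline ppFVC as response, it must include baseline ppFVC × time as well as baseline ppFVC. It is not interchangeable with the first form, because it drops participants who lack a Day 1 or a post-baseline value.

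The cost is one line in the model statement and one extra sensitivity run. No new data are needed.
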